10. EFFICACY ANALYSES

All Efficacy analysis will be conducted on the ITT set unless otherwise stated.

10.1. SARS-CoV-2 Infection Symptom Checklist

All patients will be issued a patient diary for SARS-CoV-2 Infection Symptom Checklist at screening and will be required to record it in the diary from Day 1 until Clinical recovery or Day 28 whichever comes first. After Day 28, additional recording of the diary will be required if following conditions are met:

- For patients who will achieve clinical recovery at Day 28, patients will record the diary until Day 29 to confirm whether it is maintained at least 24 hours.
- For patients who will show deterioration (at the discretion of the Investigator) after the achievement of clinical recovery, patient will record the diary until secondary achievement of clinical recovery.
- After Day 28 of regular scheduled study visit, for patients with suspicious ADE occurrence, patient will record the diary for 7 days from the day of suspicious ADE occurrence specified in [Appendix 2](#).

All patients will be instructed to complete the diary twice a day in the following time point at approximately 12-hour intervals except for screening: In the morning (between 6 and 10 AM, approximately) and in the evening (between 6 and 10 PM, approximately). The patient will be recorded once at screening. On the date of study drug administration (Day 1), the patient diary

will be recorded twice before and after the study drug administration. If screening visit date and the administration of study drug date are same, the patient diary will be recorded twice before and after the study drug administration (Day 1).

SARS-CoV-2 Infection Symptom Checklist consists of 7 symptoms and the intensity of patient’s self-aware for each symptom. The 7 symptoms are feeling feverish, cough, shortness of breath or difficulty breathing, sore throat, body pain or muscle pain, fatigue, and headache. Scores for SARS-CoV-2 infection symptom are “Absent (0)”, “Mild (1)”, “Moderate (2)”, “Severe (3)” and “Not Done”.

Clinical recovery is defined by all symptoms on the SARS-CoV-2 infection symptom Checklist are recorded as ‘absent’ or ‘mild’ in intensity for at least 24 hours. To satisfy the clinical recovery, symptoms of the moderate or severe in intensity at baseline should be scored as mild or absent, or symptoms of the mild or absent in intensity at baseline should be scored as absent, after study treatment. Patients who meet the clinical recovery criteria for at least three consecutive time points will be considered as satisfying condition of 24 hours, and achieving clinical recovery at the first time point. The three consecutive time points for each symptom can be different because the three consecutive time points will be determined excluding missing data if the results of some symptoms are missing on the SARS-CoV-2 infection symptom Checklist. However, results of all 7 symptoms have to be recorded at the first time point achieving clinical recovery. The example of a patients achieving clinical recovery on Day 14 Morning is presented the following [Table 3](#).

Table 3 Example of a Patients Achieving Clinical Recovery

	Day 14 Morning	Day 14 Evening	Day 15 Morning	Day 15 Evening
Feeling feverish	0	0	Missing	0
Cough	0	Missing	0	0
Shortness of breath or difficulty breathing	0	0	0	0
Sore throat	0	0	0	0
Body pain or muscle pain	0	0	0	0
Fatigue	0	0	0	0
Headache	0	0	0	0

The time to clinical recovery (days) will be calculated as [date/time achieving clinical recovery (or censoring) – date/time of study drug administration]. Patients who are ongoing in the study without event, with death or early withdrawal for any reason will be considered as censored at the day of their scheduled visit of interest (Day 28). Missing time of completion of diary will be assumed to be 10:00 AM and 10:00 PM for calculation of time to recovery.

The number and percentage of patients with clinical recovery up to Day 7, Day 14, and Day 28 and Censored up to Day 28 along with censoring reason will be displayed by treatment group. The 25th percentile, 50th percentile (median) and 75th percentile will be estimated from Kaplan-Meier curve for the time to clinical recovery up to Day 28 and displayed by treatment group. Kaplan-Meier plots for each treatment group will be presented.

This listing will include all data collected on the “SARS-CoV-2 Infection Symptom Checklist” page of eCRF.

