## 6.3 Efficacy Assessments

### 6.3.1 Patient Diary for SARS-CoV-2 Infection Symptom Checklist

All patients will be issued a patient diary for SARS-CoV-2 Infection Symptom Checklist at Screening and will be required to record it daily from Day 1 until clinical recovery or Day 28, whichever comes first. Patients will be instructed to complete the diary twice a day at approximately 12-hour intervals in the morning (between 6 and 10 AM, approximately) and in the evening (between 6 and 10 PM, approximately). The patient diary will be recorded once at Screening. On the date of study drug administration (Day 1), the patient diary will be recorded twice before and after the study drug administration.

The study site staff will instruct the patients on the use of the diary. Patients will be told to bring their completed diary each time they return to the study site. Study staff will review the entries in the diary at each study visit. If the patient is not compliant in regard to filling out the diary (omissions, discrepancies, or other difficulties), instructions on how to use the diary may be repeated. Study site staff should encourage the patient to complete the diary and remind the patient of the importance of following study procedures while at home.

SARS-CoV-2 Infection Symptom Checklist consists of 7 symptoms and the intensity of patient's self-aware for each SARS-CoV-2 infection symptom. The 7 symptoms of SARS-CoV-

2 infection are feeling feverish, cough, shortness of breath or difficulty breathing, sore throat, body pain or muscle pain, fatigue, and headache. Scores for SARS-CoV-2 infection symptom are absent (0), mild (1), moderate (2), and severe (3).

A full SARS-CoV-2 Infection Symptom Checklist is described in [Section 11.2](#).

Clinical recovery is defined by all symptoms on the SARS-CoV-2 Infection Symptom Checklist will be recorded as ‘absent or mild in intensity’ for at least 24 hours. To satisfy the clinical recovery, symptoms of the moderate or severe in intensity at Screening should be scored as mild or absent, or symptoms of the mild or absent in intensity at Screening should be scored as absent, after study treatment.

After Day 28, additional recording of the diary will be required if following conditions are met:

- For patients who will achieve clinical recovery at Day 28, patients will record the diary until Day 29 to confirm whether it is maintained at least 24 hours.

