5.5. Definition of Baseline

The baseline value will be considered to be the last non-missing value before the study drug administration. Post-baseline values will be considered to be all measurements collected after the study drug administration.

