13.1. Changes in the Protocol

1. To use more information in determination of the clinical recovery, ‘at Screening’ was modified to ‘at Baseline’ in the sentence “To satisfy the clinical recovery, symptoms of the moderate or severe in intensity at Screening should be scored as mild or absent, or symptoms of the mild or absent in intensity at Screening should be scored as absent, after study treatment.”.
2. Although ‘Virology analysis vendor (████████████████████)’ conducted an analysis for ‘Cell culture’, statistical analysis was not possible because results were not derived from most of the analysis, so related sentences about ‘Cell culture’ was deleted in the SAP.

14. Reference List

International Council for Harmonisation (ICH) Assembly. ICH E9: Statistical principles for clinical trials – Step 5. 01 September 1998.

US Department of Health and Human Services. (2010). National Institutes of Health, National Cancer Institute. Common Terminology Criteria for Adverse Events (CTCAE) version 5.0. Available from: <http://evs.nci.nih.gov/ftp1/CTCAE/About.html>

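### The diary may stop at recovery judged against Screening, but the SAP judges recovery against baseline, so some patients with a residual mild symptom cannot be assessed yet are carried to Day 28 as not recovered

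*SAP*

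**What the plan says.** **Protocol 6.3.1.** Patients receive the diary at Screening and "will be required to record it daily from Day 1 until clinical recovery or Day 28, whichever comes first". Recovery means that all seven symptoms are absent or mild for at least 24 hours, with a further condition for each symptom that depends on the Screening score. The lenient branch is that "symptoms of the moderate or severe in intensity at Screening should be scored as mild or absent". The strict branch is that "symptoms of the mild or absent in intensity at Screening should be scored as absent, after study treatment". Recording resumes after recovery only if the patient deteriorates in the investigator's view, or later for suspected antibody-dependent enhancement.

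**SAP 10.1 and 5.5.** The SAP repeats the stopping rule but replaces Screening with baseline in both branches; the strict branch becomes "symptoms of the mild or absent in intensity at baseline should be scored as absent, after study treatment". SAP 5.5 defines baseline: "The baseline value will be considered to be the last non-missing value before the study drug administration". For the diary this is normally the Day 1 pre-dose entry, because "On the date of study drug administration (Day 1), the patient diary will be recorded twice before and after the study drug administration". The 24-hour condition is met by three consecutive time points.

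**SAP 13.1.** The switch is declared, with the reason "To use more information in determination of the clinical recovery". The diary stopping rule is not mentioned.

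**Patients without an event.** "Patients who are ongoing in the study without event, with death or early withdrawal for any reason will be considered as censored" at Day 28 (SAP 10.1). Percentages use every patient in the treatment group (SAP 5).

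**The concern.** The rule that decides when data collection may end and the rule that decides whether the patient recovered use different reference scores. Screening can be up to seven days before dosing, so the two scores can differ. Mild disease is defined at entry by oxygen saturation and no need for oxygen, not by symptom score (Protocol 4.2), so moderate or severe scores at Screening are possible.

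Where the SAP target is stricter than the protocol target, a patient may properly stop recording before the SAP question is answered. The Kaplan-Meier analysis then treats that patient as followed without recovery to Day 28, although no diary entry supports this. The stated aim was to use more information, but for these patients the protocol did not require the entries that the SAP needs. The results affected are time to clinical recovery and the Day 7, 14 and 28 recovery proportions.

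**Working it through.** **1. The plan's own example.** I applied the SAP rule as written: all seven symptoms recorded at the first time point, and each symptom meeting its target at three consecutive non-missing time points. Applied to SAP Table 3 it gives Day 14 Morning, as the SAP states, whichever reference score is assumed. The example therefore does not distinguish the two references.

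**2. When the targets differ.** A reference of moderate or severe gives the target mild or absent. A reference of absent or mild gives the target absent. For one symptom there are 4 × 4 = 16 pairs of Screening and baseline scores:

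| Change, Screening to baseline | Pairs | SAP target against protocol target |
|---|---|---|
| Moderate or severe to mild or absent | 4 | Stricter |
| Severe to moderate; mild to absent | 2 | Same |
| No change | 4 | Same |
| Absent to mild; moderate to severe | 2 | Same |
| Absent or mild to moderate or severe | 4 | Looser |

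So 4 of the 6 improving pairs have a stricter SAP target, and 4 of the 6 worsening pairs have a looser one. These are counts of possible score pairs, not patient frequencies.

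**3. One patient followed through.** Cough is moderate at Screening, mild pre-dose, mild for the first ten post-dose entries and then absent. The other symptoms are absent throughout. Entries are 12 hours apart, starting on the evening of Day 1.

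- Protocol reference (moderate): the target is met from entry 1 and confirmed at entry 3, so the diary may stop there, on Day 2.
- SAP reference (mild), diary continued: cough is first absent at entry 11, which is 10 × 12 = 120 hours after entry 1, or about Day 6. Recovery is dated there.
- SAP reference, diary ended at entry 3: no recovery is found, and the patient is censored at Day 28.

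If cough is instead absent from entry 1, both rules give recovery at entry 1 and nothing is lost. If the scores go from severe to moderate, both rules again agree.

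**4. Size per affected patient.** The groups are 5 per CT-P59 dose and 3 × 1 = 3 pooled placebo (SAP 5.2 and 5.4).

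- CT-P59 group: 1/5 = 20.0 points.
- Pooled placebo: 1/3 = 33.3 points.

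**5. Effect on the median.** Suppose all other patients recover. With 3 of 5 affected, the curve ends at 3/5 = 0.60. With 2 of 3 affected, it ends at 2/3 = 0.67. Both stay above 0.50, so the median cannot be estimated.

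**The case against.** The strongest reply is that the change is declared in SAP 13.1, agrees with the SAP-wide definition of baseline, and concerns a secondary endpoint summarised descriptively, with no hypothesis test and no efficacy output in the first study report (SAP Appendix 5). That stands, and it limits the stakes. What was declared, however, is the new reference, not its consequence for data already allowed to end.

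A second reply is that the actual stopping time is not documented. Three time points is the SAP's working rule, while the protocol says only 24 hours. Staff review the diary at visits, and in-house stay is recommended to Day 7, so some patients may record for longer, and the SAP would use those entries. This also stands: stopping at the third entry is what the protocol permits, not an observed fact.

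A third reply is that the SAP already shows censoring reasons and lists every diary entry, so an early end could be found among 18 patients. That is partly right, but the only reasons named are continuing without event, death and withdrawal.

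A reader might also infer more than the documents support:

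- **That everyone who improved before dosing is lost.** Two of the six improving pairs have identical targets, and a symptom absent for three time points satisfies both rules. With same-day Screening and dosing there is a single reference.
- **That recovery is understated overall.** Worsening before dosing loosens the SAP target and can bring recovery forward. The documents give no frequency for either direction.
- **That the timing error is about 26 days (28 − 2).** This subtracts a recovery time under one definition from a censoring time under another. Censoring at Day 28 is not a recovery time.
- **That the number affected depends only on the Screening-to-dose interval and not on CT-P59.** A patient is affected only if a symptom is still mild after dosing, and treatment may influence that.

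**Conclusion.** The mismatch is real and follows from the text of the two documents. A patient is affected when at least one symptom fell from moderate or severe at Screening to mild or absent pre-dose, and that symptom is still mild when the diary is allowed to stop. From the data then collected, such a patient cannot meet the SAP definition, yet is counted as not recovered through Day 28.

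The per-patient sizes of 20 and 33 points assume that the patient would otherwise have counted as recovered by the day in question. A symptom truly still mild at Day 7 is correctly not recovered at Day 7 under the SAP. The conclusion also assumes that recording ends when the protocol permits. The number of affected patients and the net direction of the effect are unknown. The point deserves correction because the groups are very small and the tables would not show that the cause is missing diary data. It does not bear on the primary safety objective.

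**What to change.** In SAP 10.1, and noted in SAP 13.1:

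1. Add time to clinical recovery and the Day 7, 14 and 28 proportions using the protocol's Screening reference, which governed diary collection. Present them beside the baseline-referenced version; the declared baseline reference need not be withdrawn.
2. In the baseline-referenced version, report by treatment group the number of patients whose diary ended before SAP-defined recovery.
3. Show those patients as not assessable after their last entry. In the Kaplan-Meier analysis, censor them at the last diary entry instead of Day 28. State that this censoring may be informative, because the diary ended on account of improvement.

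The cost is SAP wording, one extra programmed version of an existing table and curve, and two sets of recovery figures to present and explain.

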### 4.2 Inclusion Criteria

Each patient must meet all of the following criteria to be randomized in this study:

1. Adult male or female patient, aged between 18 to 60 years (both inclusive).
2. Patient with laboratory confirmed SARS-CoV-2 infection by RT-PCR at Screening.

**Note:** But, if the patient had RT-PCR result confirming SARS-CoV-2 infection prior to obtaining written informed consent (but no more than 7 days from the onset of symptoms), the result can be allowed.

**Note:** During the Screening Period, only one retest for RT-PCR will be allowed, if study drug can be administered no more than 7 days from onset of symptom based on the retest results.

3. Patient has mild conditions meeting all of the following criteria:
  - a. Oxygen saturation  $\geq 94\%$  on room air.
  - b. Not requiring supplemental oxygen.
4. Patient has one or more of the following SARS-CoV-2 infection associated symptoms within 7 days prior to the study drug administration:
  - a. Feeling feverish
  - b. Cough
  - c. Shortness of breath or difficulty breathing
  - d. Sore throat

- e. Body pain or muscle pain
- f. Fatigue
- g. Headache
- h. Chills
- i. Nasal obstruction or congestion
- j. Loss of taste or smell
- k. Nausea or vomiting
- l. Diarrhea

5. Patient has one or more of the following SARS-CoV-2 infection associated symptoms present within 48 hours prior to the study drug administration:

- a. Feeling feverish
- b. Cough
- c. Shortness of breath or difficulty breathing
- d. Sore throat
- e. Body pain or muscle pain
- f. Fatigue
- g. Headache

6. Onset of symptom is no more than 7 days prior to the study drug administration. Onset time of symptom is defined as the time when the patient experienced the presence of at least one symptom of the SARS-CoV-2 infection.

7. Patient with a body weight between 50 kg and 100 kg (both inclusive) and a BMI of  $\geq 18.0$   $\text{kg}/\text{m}^2$ .

8. Patient is able to understand and to comply with protocol requirements, instructions, and restrictions.

9. Patient voluntarily agrees to participate in this study and has given a written informed consent prior to undergoing any of the Screening procedures.

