Treatment Period (Day 1 to prior to End-of-Treatment Visit): Inclusion and exclusion criteria will be re-confirmed on Day 1. If it is concluded that the patients are not eligible in Day 1 assessments, the patient will be considered as Screening failure even if he/she was eligible based on assessments results performed during Screening Period. Patients will be randomized in 5:1 ratio to receive CT-P59 or placebo once all eligibility criteria have been confirmed. Patients will receive a single dose of CT-P59 or placebo on Day 1. All patients will be admitted to the study center on Day 1 and it is recommended to be confined up to Day 7. In-house stay period can be determined by Investigator considering the isolation regulation and/or public health capacity of the country, however all patients should be confined to the study center for at least 72 hours (until completion of all assessments on Day 3). After discharge, the consecutive study visits will be carried out on an out-patient basis. During the isolation period according to the local regulation, patients will visit the study center using the transportation provided by Sponsor.

End-of-Treatment Visit (Day 90): End-of-treatment (EOT) visit assessments will be performed on Day 90. If a patient is early terminated from the study, the patient will be asked to return to the study center as soon as possible for the safety assessments predefined for EOT visit.

Follow-Up Period (From End-of-Treatment Visit to Day 180): For all patients including a patient who early terminated from the study, each telephone call follow-up will occur bi-weekly from 2 weeks after the EOT visit to Day 180. During the Follow-Up Period, SARS-CoV-2 infection related signs and symptoms will be assessed by telephone call to capture the suspicious antibody dependent enhancement (ADE) occurrence. For patients with suspicious ADE occurrence, additional assessments will be conducted on unscheduled visit.

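### The clinical recovery rule does not require a symptom at baseline, so a patient who cleared before dosing and stays clear for three diary entries is dated as recovered at the first post-dose entry

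*SAP*

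**What the plan says.** Baseline (SAP 5.5): "The baseline value will be considered to be the last non-missing value before the study drug administration". On Day 1 the diary "will be recorded twice before and after the study drug administration" (SAP 10.1), so the reference is normally the pre-dose entry of that day.

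Threshold (SAP 10.1): a symptom moderate or severe at baseline must fall to mild or absent. For the rest, "symptoms of the mild or absent in intensity at baseline should be scored as absent, after study treatment".

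Persistence and dating (SAP 10.1): "Patients who meet the clinical recovery criteria for at least three consecutive time points will be considered as satisfying condition of 24 hours", and the patient is taken as "achieving clinical recovery at the first time point". All seven symptoms must be recorded at that point. Time to recovery runs from study drug administration.

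Population (SAP 10): "All Efficacy analysis will be conducted on the ITT set unless otherwise stated". SAP 5.4.1 defines ITT as all randomized patients, and Protocol 7.4.5 also names ITT for efficacy.

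Eligibility (Protocol 4.2, criterion 5): "Patient has one or more of the following SARS-CoV-2 infection associated symptoms present within 48 hours prior to the study drug administration". The seven symptoms listed there are those of the checklist. SAP 4.1 adds "Inclusion and exclusion criteria will be re-confirmed on Day 1", but the criterion keeps its 48-hour look-back when it is re-checked.

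**The concern.** A time-to-recovery analysis assumes that each patient starts in the unrecovered state. Here a patient can be eligible, be randomized and already be free of all seven symptoms at the last pre-dose entry. A symptom scored absent before and after dosing satisfies the rule with no change. Nothing in SAP 10.1 excludes such a patient, censors the patient or reports the patient separately.

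The Kaplan-Meier curve and the Day 7, 14 and 28 proportions would then show a very fast recovery after treatment where the recovery came before it. In a CT-P59 group this flatters the drug; in placebo it hides a difference. Groups of five and three cannot dilute one misplaced event, and with no test planned these summaries are all that the endpoint delivers. The diary also stops at clinical recovery and restarts only for deterioration judged by the investigator or for suspicious ADE, so little later diary data may exist to qualify the early event.

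**Working it through.** **1. Reproduce the plan's own example.** SAP Table 3 dates recovery to Day 14 Morning. All seven symptoms are recorded as 0 there. Feverishness then has non-missing zeros on Day 14 Evening and Day 15 Evening; cough has them on Day 15 Morning and Day 15 Evening; the other five have them at the next two entries. Each symptom has three consecutive non-missing qualifying entries, so the rule returns Day 14 Morning, as stated. The answer is the same whether the baseline scores are all 0, all 1 or all 2.

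**2. Apply the rule to a baseline of seven zeros.**
- All post-dose entries 0: recovery at post-dose entry 1.
- Mild cough at entry 2 only: recovery at entry 3.
- Mild cough at entry 3 only: recovery at entry 4.
- Two clear entries, then persistent mild cough: no recovery.
- Only two post-dose entries: no recovery.

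If dosing falls between 08:00 and 17:00 (assumed) and the first post-dose entry between 18:00 and 22:00, the event time lies between (18 − 17)/24 = 0.04 and (22 − 8)/24 = 0.58 days.

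**3. Compare with the protocol's reference.** Protocol 6.3.1 uses the Screening score. A post-dose score of 0 qualifies whether the reference is 0, 1, 2 or 3, so the all-clear patient is dated to entry 1 under either document. If cough was moderate at Screening, absent at baseline and mild after dosing, the protocol accepts it (reference 2, score 1) and the SAP does not (reference 0, score 1).

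**4. Size for the proportions.** Inputs: five CT-P59 patients per cohort and one placebo patient in each of three cohorts, pooled (SAP 4.1, 5.4). Let k be the number of other patients recovered by the day in question, and compare the plan with leaving one such patient out.

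CT-P59 group, (k+1)/5 − k/4:
- k = 0: 20% − 0% = 20 points
- k = 1: 40% − 25% = 15
- k = 2: 60% − 50% = 10
- k = 3: 80% − 75% = 5
- k = 4: 100% − 100% = 0

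Pooled placebo, (k+1)/3 − k/2:
- k = 0: 33% − 0% = 33 points
- k = 1: 67% − 50% = 17
- k = 2: 100% − 100% = 0

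**5. Size for the quartiles (illustration; all times assumed).** Put the symptom-free patient at 0.4 day and the others at 4, 6, 8 and 10 days as needed. Each quartile is the earliest time at which the curve reaches the level.
- Placebo, one of three: 0.4 / 4 / 6 days as planned, 4 / 4 / 6 with the patient left out.
- CT-P59, one of five: 4 / 6 / 8 both ways. If the convention averages adjacent times when the curve meets the level exactly, the values without the patient are 5 / 7 / 9, a shift of one day.
- CT-P59, two of five: 0.4 / 4 / 6 as planned, 4 / 6 / 8 with both left out.

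**6. Frequency.** The documents give no rate of symptom-free baselines. With assumed rates p of 5%, 10% and 20% and independent patients, the chance of at least one among 18 is 1 − (1 − p)^18 = 60%, 85% and 98%.

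**The case against.** The best case for leaving the plan alone has four parts.

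- **The rule has its own safeguard.** An all-absent baseline is not enough: all seven symptoms must be recorded at the first point and stay absent over three entries, about 24 hours. This stands, and it limits the point to patients who were clear and remained so.
- **These patients were ill.** Criterion 5 guarantees a checklist symptom within two days of dosing. This also stands. A reader might infer that the rule counts patients who never had the condition; the documents do not support that. The fault is one of timing: a real recovery before treatment is credited to the period after it.
- **The SAP did not create the problem.** SAP 13.1 replaced Screening by baseline in the definition, and a reader might blame that change. Step 3 shows that all-absent entries satisfy both versions and that the SAP is stricter where a symptom returns as mild.
- **The consequence is small.** The endpoint is secondary and descriptive, SAP 5.2 states no formal hypothesis, Appendix 5 lists no recovery output for the first CSR, and the listing of all checklist data would reveal such a patient. This supports a low severity. It does not repair the summary tables and curves, which are what most readers will use.

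**Conclusion.** The point holds as a minor defect. Followed as written, SAP 10.1 dates to the first post-dose entry a patient who was symptom-free before dosing and stayed so for three consecutive entries, and nothing in either document prevents or flags this.

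One such patient raises a recovery proportion by at most 20 points in a CT-P59 group or 33 in pooled placebo. A reader might take these maxima as the bias to expect. They apply only when nobody else in the group has recovered, and the effect falls to 0 once everyone has, which is most likely at the later time points. The quartiles may move or not, depending on the group, the number of such patients and the percentile convention.

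These sizes assume planned group sizes and leaving the patient out as the comparator. The number of such patients, and the groups in which they fall, cannot be known from the documents. No error rate or sample size is affected.

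**What to change.** Amend SAP 10.1 as follows:
- Report per treatment group the number of patients with all seven checklist symptoms absent at baseline.
- Present time to recovery and the Day 7, 14 and 28 recovery proportions for ITT patients with at least one of the seven symptoms present at baseline, next to the full-ITT version that the protocol specifies.
- Record the addition in SAP 13.

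Selection uses a pre-dose score already collected, so treatment cannot influence it. SAP 5 allows updates before database hard lock. Because the code is broken after the Day 14 lock (SAP 5.3), the change should be made before then so that it cannot appear data-driven.

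The cost is one or two extra outputs and possibly one or two fewer patients in the restricted analysis. That loss matters most in placebo, where one exclusion leaves two patients; keeping the full-ITT result alongside covers this.

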5.2. Sample Size

The total sample size of 18 patients is not based on a formal statistical hypothesis. A sample size justification based on statistical hypothesis is not relevant in this study. The proposed number of 6 patients (5 patients for CT-P59 and 1 patient for placebo) in each cohort is set empirically based on sample sizes in other Phase 1 studies investigating the safety and tolerability of their study drugs and is considered to be sufficient to achieve the objective of the study.

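### The recovery rule in SAP 10.1 skips missing symptom results without limit, so 24 hours of recovery can be confirmed across an unobserved gap of any length

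*SAP*

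**What the plan says.** Protocol 6.3.1 states the definition: "Clinical recovery is defined by all symptoms on the SARS-CoV-2 Infection Symptom Checklist will be recorded as" absent or mild for at least 24 hours. Symptoms that began as moderate or severe may end as mild; the others must be absent. The Protocol has no rule for missing scores.

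SAP 10.1 makes the definition operational:

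- **Frequency.** "All patients will be instructed to complete the diary twice a day", about 12 hours apart, in morning (6 to 10) and evening (6 to 10) windows.
- **The 24 hours.** "Patients who meet the clinical recovery criteria for at least three consecutive time points will be considered as satisfying condition of 24 hours", with the patient "achieving clinical recovery at the first time point".
- **Missing results.** "the three consecutive time points will be determined excluding missing data if the results of some symptoms are missing" on the checklist. The three points may differ from one symptom to another.
- **Safeguard.** All seven symptoms must be recorded at the first of the three points. Nothing similar is asked of the confirming points.

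Table 3 gives one worked example, with a single missing result for each of two symptoms. The only other rule in SAP 10.1 for missing diary data fills in a missing clock time, not a missing score. Neither document limits the number of skipped results or the elapsed time.

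**The concern.** The three-point rule stands in for 24 hours only because scheduled entries are 12 hours apart. Once missing results are skipped without limit, that link is lost: three results spread over a week confirm 24 hours as readily as three results from one day to the next. Because the points may differ by symptom, the seven symptoms also need not be shown to qualify over the same period.

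Gaps are foreseeable. SAP 10.1 has a Not Done category, and Protocol 6.3.1 plans for omissions. It also lets recording stop when the patient's condition prevents it, with sedation for ventilation as the example. If wholly missed entries are skipped, a patient with one qualifying entry, then a period too ill to record, then two qualifying entries would be dated as recovered before the deterioration.

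At stake are the time to clinical recovery and the recovery proportions at Days 7, 14 and 28, in groups where one patient carries much weight.

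**Working it through.** **Inputs.** Two entries a day, 12 hours apart; three qualifying results; date at the first; missing results skipped (all SAP 10.1). Group sizes follow from "5 patients for CT-P59 and 1 patient for placebo" per cohort (SAP 5.2) with placebo pooled over three cohorts (SAP 5.4): 5 per dose group and 3 on placebo. No missingness rate is given.

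**1. The plan's own example.** In Table 3, cough is missing on Day 14 Evening, so its three results are Day 14 Morning, Day 15 Morning and Day 15 Evening. Fever is missing on Day 15 Morning, so its three are Day 14 Morning, Day 14 Evening and Day 15 Evening. All seven symptoms are recorded on Day 14 Morning. Applying the rule gives recovery on Day 14 Morning, as the SAP states. For those two symptoms the nominal span is 36 hours, not 24.

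**2. Longer gaps.** Take a qualifying Day 5 Morning entry, then k missing results (one symptom blank is enough), then qualifying results.

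- Span accepted as 24 hours = 12 × (k + 2) hours.
- A rule with no skipping dates recovery at the first result after the gap, which is (k + 1)/2 days later for k ≥ 1.

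| k | Span accepted (h) | Date under SAP 10.1 | Date with no skipping | Difference (days) | Date with at most one skip |
|---|---|---|---|---|---|
| 1 | 36 | Day 5 Morning | Day 6 Morning | 1.0 | Day 5 Morning |
| 2 | 48 | Day 5 Morning | Day 6 Evening | 1.5 | Day 6 Evening |
| 4 | 72 | Day 5 Morning | Day 7 Evening | 2.5 | Day 7 Evening |
| 7 | 108 | Day 5 Morning | Day 9 Morning | 4.0 | Day 9 Morning |
| 14 | 192 | Day 5 Morning | Day 12 Evening | 7.5 | Day 12 Evening |

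The extreme allowed by the text is a first qualifying entry on Day 1 Evening with the next results on Day 28 Morning and Evening: k = 26 × 2 = 52, and the span is 12 × 54 = 648 hours, or 27 days.

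**3. Effect on a median (assumed data).** A patient dosed on Day 1 qualifies on Day 5 Morning; the next cough results are on Day 10 Morning and Evening. The missing cough results number 1 + 4 × 2 = 9, so the span is 12 × 11 = 132 hours. SAP 10.1 measures time from dosing, so Day 5 is about 4 days and Day 10 about 9 days. The 9-day figure assumes a complete Day 10 Morning entry and a further qualifying cough result on Day 11.

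- Dated at Day 10: times 3, 6, 9, 11, 14; median 9.
- Dated at Day 5: times 3, 4, 6, 11, 14; median 6.

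**4. Effect on a proportion.** The same patient changes from not recovered to recovered by Day 7. That is 1/5 = 20 percentage points in a dose group, or 1/3 = 33.3 points on placebo.

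**5. How often (assumed).** If each result is missing independently with probability p, and the first is observed, then P(no skip) = (1 − p)² and P(exactly one skip) = 2p(1 − p)². For one symptom:

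| p | At least one skip | At least two skips |
|---|---|---|
| 5% | 9.8% | 0.7% |
| 10% | 19.0% | 2.8% |
| 20% | 36.0% | 10.4% |
| 30% | 51.0% | 21.6% |

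Real missingness is likely to cluster, so these figures give a range and are not an estimate.

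**The case against.** The strongest case against is that the rule has a real safeguard and the stakes are small. The dated entry must be complete and qualifying, so it was observed. If recovery persisted through the gap, the first point is the right date. The missing-data sentence speaks of some symptoms being missing, and Table 3 shows one blank item per affected entry; a nine-result gap then needs one symptom left blank nine times running. Confinement is recommended to Day 7 and required for at least 72 hours (Protocol 3.4.2), and staff review the diary at each visit. No hypothesis is tested: "The total sample size of 18 patients is not based on a formal statistical hypothesis". The endpoint is absent from the first-CSR outputs in SAP Appendix 5, and all diary data will be listed.

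Most of this stands and narrows the point. None of it supplies a limit: supervision makes long gaps less likely but does not bound them, and a listing does not change the computed time.

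A reader might also infer more than the documents support:

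- *That groups with poorer diary compliance will look faster.* A missing symptom at a candidate first point delays recovery, so the net direction is undetermined. The study is double-blind, and nothing suggests that compliance differs by group.
- *That the SAP says wholly missed entries are skipped.* It is silent on this.
- *That recovery means freedom from symptoms.* Mild is allowed where baseline was moderate or severe.
- *That Table 3 shows longer gaps were not intended.* It is labelled an example, and no text makes it a limit.

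**Conclusion.** The concern holds in this form. As written, SAP 10.1 can accept a span of days as 24 hours of recovery, and it dates recovery too early if symptoms returned unobserved in the gap. It leaves open how wholly missed entries are treated. One affected patient can shift a recovery proportion by 20 points (n = 5) or 33.3 points (n = 3). In the assumed example, one patient moves a group median from 9 to 6 days.

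The example's times are invented and the frequency is unknown. The endpoint is secondary and descriptive, so no error rate or power is affected, and the primary safety objective is untouched. This is a cheap improvement.

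**What to change.** Add to SAP 10.1: *For each symptom, at most one scheduled (nominal) time point may be skipped within the three qualifying results, whether the symptom or the whole entry is missing; otherwise recovery is not confirmed at that time point.*

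This keeps Table 3 at Day 14 Morning (nominal span 36 hours) and settles the treatment of wholly missed entries. Counting scheduled time points is safer than a 48-hour clock limit. Two skips span exactly 48 nominal hours, and with four-hour entry windows the actual span is 44 to 52 hours, so the time of completion would decide the result.

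The cost is one sentence and one program condition. SAP Section 5 allows an update before database hard lock. It is best made before the randomization code is broken for the first CSR (SAP 5.3), because the recovery analysis comes later.

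The downside should be stated. Some patients with gaps will have later recovery times. The diary stops at clinical recovery, so a patient who stopped after meeting the uncapped rule may have no further entry and be censored at Day 28. If the patient in the example stopped after Day 10 Evening, the group would be 3, 6, 11, 14 and 28 (censored), and the Kaplan-Meier median would be 11 days, not 9. The uncapped rule should therefore also be reported as a sensitivity analysis.
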